There are few available tools on how to implement an EM program, particularly in an acute cardiovascular unit. A lack of written protocols or guidelines, as well as insufficient clinician knowledge, has been identified as a barrier to implementing EM in critical care units.¹⁸

6. Patient positioning and activity in patients with acute cardiovascular disease: Precise identification of patient position (lying, sitting, and standing) and physical activity using body-worn sensors is now possible due to improvement in accelerometer technology. Accelerometry has been validated in numerous populations, including in the ICU, mainly in the context of mechanically ventilated patients.³⁰ However, previous studies in the ICU were limited by small sample sizes and short duration of patient monitoring, ranging from 60 minutes to 48 hours, and monitoring did not extend beyond ICU unit stay.³⁰ *There are also no studies in the literature specifically looking at positioning and activity in patients with acute CV disease.* It is important to understand the time spent in the different mobility positions and the relationship with functional outcomes in older adults with acute CV disease. Decreasing the duration of time spent in a lying position is a potentially modifiable factor.

V. PRELIMINARY STUDIES

During my Cardiac Intensive Care fellowship at Cedars-Sinai Medical Center in Los Angeles, CA, I participated in the EM program and instituted frailty screening in the CICU. We used a level of function (LOF) assessment tool in the EM program that ranged from 1 to 5, where 1 was bedbound and 5 was ability to walk > 50 feet (see sidebar). Preliminary analysis of the retrospective cohort of 264 patients with acute cardiovascular disease undergoing EM showed that 90 (34.1%) patients were frail, 65 (24.6%) were vulnerable, and 109 (41.3%) were not frail. We found a moderate correlation between prehospital LOF and frailty ($r = -0.580, P=0.01$). Prehospital LOF was higher in nonfrail elderly than in frail elderly (mean score of 3.71 ± 0.61 vs. 2.59 ± 1.03 ; $P < 0.001$). LOF improved in both nonfrail and frail elderly during CICU stay, however, there was greater improvement in LOF in the frail group (mean increase of 0.53 vs 0.70; $P < 0.01$). The initial data analysis suggests that frailty status is a potential predictor of responsiveness to EM. Further analysis of this dataset is needed to identify other predictors of responsiveness to EM in the CICU.

Progressive Mobility	

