Prior to the implementation of the EM intervention, nurses will ascertain and record the prehospital LOF, admission LOF, and LOF on the day of CICU transfer (Appendix A), but will continue usual mobilization practices. Patients who meet eligibility criteria for the EM intervention will be prospectively enrolled over a 3-month period (“pre-intervention cohort”) by a member of the research team during CICU admission. Informed consent will be obtained by a member of the research team. Following discharge, a member of the research team will review the medical record to extract demographic data (age, sex), comorbid illnesses, primary admission diagnosis, frailty status, adverse events during mobilization (falls, dislodgements, and injuries), mobilization activities, length of critical care unit stay, length of hospital stay, mortality, and discharge location.

Intervention

On admission to the CICU, the patient’s treating nurse will assess the patient for the EM program. Patients participating in the EM program will be assessed for enrolment in our study by a member of the research team and will obtain informed consent during CICU admission (“intervention cohort”). The potential participants are likely to be competent and medically fit to be approached for informed consent as patients who are not medically fit will be excluded from the early mobilization program based on clinical factors, which include hemodynamic criteria.

The EM program consists of a progression of functional activities from LOF 0 (lowest mobility) to 5 (highest mobility). Each LOF has 3 primary activities designed to promote the patient to the next level. The nurse will begin with mobility activities based on the LOF that matches the patient’s current status. The nurse and clinical partner will attempt and/or complete each LOF activity once per shift. Physiotherapy assistance is available if required, although not obligatory. Nurses will also provide documentation and education to patients and families on

how to perform and assist with certain activities. LOF, activity attempts/completion, and adverse safety events will be recorded on an EM flowsheet. The intervention will start while the patient is in the CICU and will continue until discharge from the CICU.

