In the patients wearing the accelerometer, data will be recorded on the total time spent in each mobility position, the daily average time spent in each mobility position, the average duration of time for each bout of sitting, standing, and walking, and sleep duration. The step count will also be recorded. The change in skeletal muscle mass from CICU admission to hospital discharge will be recorded.

We will determine which covariates predict improvement in LOF (“responsiveness”) and which ones do not (“non-responsiveness”). We will assess the recovery of physical function at 1 month and 12 months as measured by the SF-36 physical component summary score. We will compare the SF-36 scores of the highest scoring tertile of LOF on hospital discharge with the lowest scoring tertile. We will also compare hospital readmission at 30 days and discharge home vs. healthcare facility.

For safety, we will record the composite and individual components of the number of falls, injuries, and dislodgements over the total number of attempted mobility activities. The results from the intervention cohort will be compared to the pre-intervention cohort for all results.

Data Collection Procedures

Following discharge, a member of the research team will capture the following hospitalization data from the electronic medical record (Chartmaxx, Quest Diagnostics, Madison, New Jersey) for each subject: age, sex, primary admission diagnosis, comorbidities, level of function assessments, CFS score, length of CICU stay, length of hospital stay, discharge location, and referral to cardiac rehabilitation.

Availability of Participants

In the fiscal year 2016-2017, there were 1,356 admissions to the JGH CICU (mean age 68 years old; 477 female (35%)). There were 1,034 patients (76.3%) age ≥ 60 years old. The mean CICU length of stay was 3.3 days and the mean hospital length of stay was 9.5 days. Only one in five patient stays was less than 24 hours in length.

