From the pilot data, we conservatively estimate that about one-third of patients will not be eligible for the study and about 70% will agree to participate. We estimate that the loss of patients to 12 month follow-up will be approximately 10% as the vast majority of CICU patients are followed by hospital-affiliated cardiologists prior to admission or are assigned to one following CICU discharge. Given these estimates, approximately 75 patients are expected to be enrolled and followed during the pre-intervention period and 300 patients are expected to be enrolled and followed during the 12 month intervention period.

Data Analysis

Since the response variable, LOF mobility, is an ordinal variable measured at different timepoints, a cumulative logit model for repeated measurements will be fitted using generalized estimating equations. The model permits us to take into consideration the structure of the correlation between the observations. The model will then be adjusted using covariates of interest, such as age, sex, EM adherence, time spent lying in bed, and illness severity score. Predictors of change in LOF during CICU stay and following hospitalization will be assessed using linear regression. Predictors of EM adherence will also be evaluated using linear regression. All statistical analyses will be performed using SAS version 9.4 by [name], a senior biostatistician affiliated with the Lady Davis Institute Center for Epidemiology.

VII. RESOURCE AVAILABILITY AND SUPPORT

The CICU at the JGH has 16 beds equipped for advanced hemodynamic support and 32 ward beds with telemetry available. Patients are admitted to the CICU mainly for acute primary cardiovascular disease.

The nurse champion's role is to attend EM team meetings, provide education to nursing and clinical partners, and ensure nursing adherence to the protocol. A review of the CICU environment conducted with physiotherapists from the EM team has ensured that the CICU is already equipped with the standard equipment necessary for patient mobilization, particularly for bedbound and immobile patients, and nurses have been trained to use the equipment.

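### Predictors of LOF improvement are to be found by linear regression of change in a bounded ordinal score, with the starting LOF neither defined nor named as a covariate

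*Combined protocol and SAP*

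**What the plan says.** Under Outcome Measures (section VI) the protocol sets the question: "We will determine which covariates predict improvement in LOF", with covariates then sorted into those that mark responsiveness and those that do not. The Data Analysis section gives the whole method in one sentence: "Predictors of change in LOF during CICU stay and following hospitalization will be assessed using linear regression". It lists no covariates and does not define the starting value for either period.

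The same paragraph begins "Since the response variable, LOF mobility, is an ordinal variable", and on that ground chooses a cumulative logit model with generalized estimating equations (GEE) for the repeated LOF values. That model is to be "adjusted using covariates of interest, such as age, sex, EM adherence, time spent lying in bed, and illness severity score". The list is open-ended, belongs to the GEE model, and names neither starting LOF nor frailty.

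The data for a better analysis exist. In the pre-intervention period "nurses will ascertain and record the prehospital LOF, admission LOF, and LOF on the day of CICU transfer", and in the intervention period LOF goes on the mobilization flowsheet. The Intervention text gives the scale as 0 to 5.

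Section V reports prehospital LOF in nonfrail and frail patients as "mean score of 3.71 ± 0.61 vs. 2.59 ± 1.03", and then "greater improvement in LOF in the frail group (mean increase of 0.53 vs 0.70", nonfrail first. It takes this as a sign that frailty may predict responsiveness, and says that the dataset needs further analysis.

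**The concern.** A patient who starts near 5 has little room to gain, and one who starts low has much. Unless the end value rises one-for-one with the starting value, change is also negatively related to the start. A covariate that goes with a low start then picks up an apparent gain even if it has no bearing on where patients end up from a given start. The same mechanism can cancel a real adverse effect.

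At stake is the responsiveness question, and frailty in particular, since sections III to V of the background already suggest that frail patients may benefit more. Leaving the starting LOF open also means that an influential modelling choice could be made after the data are seen. Treating differences between ordinal levels as numeric sits badly with the paragraph's own reason for an ordinal model.

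**Working it through.** **Inputs from the protocol.** Scale 0 to 5. Frail 90/264 = 34.1%. Admission LOF at the study site: mean 2.3, SD 1.2. Intervention cohort: 300. Preliminary gap in prehospital LOF: 3.71 − 2.59 = 1.12. Preliminary difference in gain: 0.70 − 0.53 = 0.17. The P value for that difference cannot be reproduced, because no SD of change is given.

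**Formula.** Let end value = a + b·start + c·frail + error. Then change = a + (b − 1)·start + c·frail + error. If start is left out, the frailty coefficient becomes

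c + (1 − b)·gap,

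where gap is the nonfrail minus frail mean starting LOF. With start in the model the coefficient is c, whether the response is change or the end value.

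**What would explain the preliminary result.** With c = 0, 0.17 = (1 − b) × 1.12, so 1 − b = 0.17/1.12 = 0.15. A drop of 0.15 in gain per level of starting LOF would be enough, if the prehospital gap carried over to the starting LOF used.

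**Simulation 1, set by gap.** n = 300, 34% frail, starting LOF mean 2.3 and SD 1.2, values rounded and held within 0 to 5, no frailty effect given start. Assumed: mean gain 1.0, residual SD 0.8. There were 600 runs per setting.

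| Gap | 1 − b | False extra gain, start omitted | P<0.05, start omitted | P<0.05, start included |
|---|---|---|---|---|
| 0 | 0.15 | 0.00 | 6% | 6% |
| 0.25 | 0.30 | 0.08 | 10% | 4% |
| 0.5 | 0.15 | 0.11 | 20% | 5% |
| 0.5 | 0.30 | 0.17 | 31% | 4% |
| 1.12 | 0 | 0.10 | 16% | 7% |
| 1.12 | 0.15 | 0.23 | 63% | 6% |
| 1.12 | 0.50 | 0.56 | 99.5% | 5% |

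The formula gives 0.15 × 1.12 = 0.17 for the sixth row; the bounded scale adds the rest. The fifth row shows the effect of the bounds alone.

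**Simulation 2, set by correlation.** Start = 2.3 + 1.2z; end = 3.6 + b(start − 2.3) + 0.9e; both rounded and held within 0 to 5. Frail is the top 34% of a latent variable correlated with z. Correlation, b and the 0.9 are assumed.

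- Correlation −0.1: P<0.05 in about 9% to 14% of trials.
- Correlation −0.2 to −0.58 with b from 0.3 to 0.7: false extra gain of 0.15 to 0.79 levels, P<0.05 in 22% to 100%.
- b of 0.85 to 1.0 with correlation −0.2: 9% to 15%.
- Start included, measured without error: about 3% to 8%.

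**A hidden adverse effect.** With a true c of −0.3, gap 1.12 and 1 − b = 0.15, the formula gives −0.3 + 0.168 = −0.13, and the bounded simulation −0.07. The effect was detected in 12% of trials without the start and 77% with it. In simulation 2, with c = −0.2, b = 0.5 and correlation −0.4 or −0.58, the change regression reported a gain of +0.22 to +0.40.

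**The case against.** **Silence is not exclusion.** A reader might infer that the plan has decided to leave starting LOF out. It has not: it lists no covariates for this regression, and the GEE list is open. This stands. The fault is that the start is neither defined nor named.

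**The preliminary gap may not apply.** The 1.12 gap and r = −0.580 concern prehospital LOF, on a 1 to 5 scale, in another unit. No frailty split is given for admission LOF. Excluding prehospital LOF 0 to 2 should narrow the gap here. At correlation −0.58, an artefact as small as the observed 0.17 needs b near 1.0 (false gain 0.165, P<0.05 in 34%), unless a true adverse effect offsets a larger artefact. This also stands, so the strong-link figures are an upper end and not a forecast.

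**Adjustment is not neutral.** LOF is a bedside rating and frailty is not randomised. With rating error SD 0.5, correlation −0.58 and b of 0.85 to 1.0, the adjusted model gave a false negative frailty coefficient (−0.23 to −0.26), significant in 46% to 54% of trials, against 14% to 39% for raw change. In a contrived case with no ceiling, gap 1.12, error SD 0.3 to 0.5 and equal true change in both groups, the figures were 50% to 82% against about 4%. This is a reason to keep change in the report, not to leave the sentence as it is.

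**The stakes are limited.** The primary outcome is LOF level under an ordinal model, and this regression does not touch it. That is correct and bears on priority.

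**Conclusion.** The point holds as a weakness of method, and correcting it is a cheap improvement. The plan commits the responsiveness question to a model in which the starting level can distort any covariate linked to it, in either direction, and does not say how the start is handled. The false-positive rate for frailty runs from about 9% with a weak link to nearly 100% with a strong one, against about 3% to 8% with an error-free start in the model. It falls to the nominal 5% as the gap in starting LOF goes to zero. The range rests on assumed correlation, slope, mean gain and residual SD, none of which the protocol gives for the starting LOF.

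Two stronger readings are not supported. The documents do not show that the preliminary frailty result is an artefact: it has the pattern that an artefact would produce, and section V words it as tentative. Nor do they show that the trial will report a false predictor, since that depends on a gap in starting LOF that is not known for this population.

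**What to change.** Replace the sentence on predictors of change with:

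> Predictors of LOF at the end of each period (CICU discharge, 1 month, 12 months) will be examined with a cumulative logit model of the end value, with the starting LOF as a covariate: admission LOF for the CICU period, and CICU-discharge LOF for the later periods. Patients who start at level 5 are included. Change in LOF will be reported alongside, by starting level. Predictors will be described as associations.

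The covariates to be tested, frailty among them, should be listed in the same place.

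The cost is a few lines of analysis text. The LOF values are already recorded, the planned software fits the model, and no patients are added. The small downside is the possible bias in the opposite direction when LOF is rated with error, which is why both results should be shown.

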Appendix A: **Validation Studies of Segmental Multi-Frequency Bioimpedance (BIA)**

Study	N	Population	Fat Free Mass Mean ± SD	Correlation vs. DXA R	Bland-Altman vs. DXA Mean Difference (95% CI)
Alves 2014	55	Stable heart failure patients	57 ± 9 ♂ 39 ± 6 ♀	0.93	+0.1 (-4.9, +5.1)
Kim 2013	129	Community-dwelling women aged 75+	30.6 ± 3.5 ♀	0.92	-2.1 (-2.8, -1.8)
Furstenberg 2010	53	Hemodialysis patients	45.7 ± 10.1	-	+0.5 (-0.7, +1.7)
Bosy-Westphal 2013	254	Healthy volunteers aged 18-65	65.4 ± 6.6 ♂ 55.4 ± 11.8 ♀	0.99	+0.05 (-3.7, +3.7)
Leahy 2012	403	Healthy volunteers aged 18-29	66.7 ± 6.4 ♂ 46.2 ± 4.0 ♀	-	+0.6 (-4.9, +6.0) ♂ +2.0 (-2.1, +6.2) ♀
Ling 2011	484	Middle-aged adults from Leiden Longevity Study	63.6 ± 7.0 ♂ 46.5 ± 5.2 ♀	0.98	-1.5 (-4.0, +1.1) ♂ -0.8 (-3.2, +1.6) ♀
Shafer 2009	132	Healthy volunteers aged 19-72	68.1 ♂ 45.9 ♀	-	+0.3
